## 4.3.2 Forecasting algorithms.

The core of the intervention is a ML-based summary of predicted postoperative risks, the change in those risks during the case, the most relevant input variables for ML predicted risks, expert-curated important variables, and other "explanatory tools" derived from the ML risk prediction method. Transcribed below from the TECTONICS (IRB# 201903026) protocol is the method for generating ML risks from preoperative and intraoperative data (internal citations omitted):

We are integrating the machine-learning forecasting algorithms for adverse outcomes with our other alerting tools, and will be testing and improving them over the course of the study. The feasibility of this integration is supported by a previous successful trial, where members of our investigative team, using live data from the EHR, implemented machine learning algorithms to guide a rapid response team in medical wards. Furthermore, the results of the prior study provide strong support for using the multi-path convolutional neural network (MPCNN) model to build and regularly improve predictive machine-learning algorithms that will be used to forecast adverse outcomes (e.g., renal failure, respiratory failure, delirium, death) in the TECTONICS trial. We found that our algorithms, which are based on extensive patient information (i.e., demographic characteristics [including sex as a biological variable], surgical risk, comorbidities) as well as time series physiological data (e.g., blood pressure, temperature, heart rate) predict outcomes such as death with high area under receiver operator characteristics curve (~90%), acceptable sensitivity (~50%) and excellent specificity (~95%). These algorithms will augment dynamic risk assessment in the ACT. Our MPCNN algorithms are unusual in that they are designed to handle heterogeneous data types, including numerical features, categorical features, and multivariate time series. By integrating feature preprocessing and model learning phase together, our algorithms are able to jointly learn complex feature interactions among different data types, ultimately improving predictions of adverse perioperative outcomes (such as in-hospital mortality, postoperative acute renal failure, postoperative respiratory failure). As our models accept raw data directly, high quality real-time prediction can be achieved.

The machine learning algorithms that will be used as part of the TECTONICS trial were developed, tested, and validated using multiple studies. We have tried many other algorithms, including in our ACTFAST2 study, and convolutional neural network (CNN) gives the best overall performance. We recently compared our CNN method with more than 10 other state-of-the-art time-series prediction algorithms and showed that CNN gives the best predictive performance. Our team members have been pioneers in the use of machine learning to predict adverse patient trajectories in the setting of critical illness. We have well-developed sophisticated machine learning techniques, and the application of our algorithms to the intraoperative setting – where changes in patient trajectory occur very rapidly – is a novel application of this technology.

[figure not shown]
#### 4.3.3 Other Interventions

We will notify the PACU anesthesiology resident when report cards are generated for high-risk patients. This notification will occur by SMS to a BJH-issued phone which is passed between residents at each shift. The notification does not contain PHI or PII, only that a particular OR has a high-risk patient.

Discussed in the Outcomes section, the study also includes a survey for providers, which we mention here because of its patient-information security implications. The Epic BPA (and printout) will contain a patient-specific link and QR code to a RedCap survey. This survey contains no PII, only a randomized study ID.

Information flow and security. To minimize the risk of protected health information (PHI) or personally identifiable information (PII) leaking from the health-care environment, we will restrict communications to providers to secure and auditable delivery modes. A diagram of the flow of information is included in Figure 6. There are 3 distinct flows of information: from the ML server and ACT tower to the PACU provider notifying them that a high-risk patient is emerging (the alert), from the ML server and ACT to the healthcare provider in the body of the report card, and between the postoperative provider to the research coordinator with their survey responses (provider survey).

The alert is designed to include minimal potentially sensitive information. It will contain the location of the patient (operating room, PACU bay destination) and that the risk of patient decompensation is elevated. The name, MRN, date of birth, or other identifiers are not included.

The only individuals who can access the report card (which contains no PII) are (1) Epic users who access the patient's chart (2) pre-approved users in the ACT who log in with their wustl-key (3) individuals reading the patient's paper chart. The ML server will be behind the WashU-BJH firewall, and therefore only accessible from authenticated users on campus or logged in via VPN. Access to the report card will be logged by IP address.

The survey is an outcome measurement, discussed in more detail below. The survey link is patient and date specific using the study ID, but does not contain the patient name or other identifiers. The survey link will be contained in the Epic BPA and the print-out in the form of a QR code; because study IDs are long and randomized they are functionally un-guessable. Versions of Android and iOS since 2018 include QR code and web-link identification from the

default camera application. Providers can also use BJH bedside computers, which are equipped with scanners that read QR codes.

#### 4.3.4 Modifications

We anticipate that the form of the report template will vary as we conduct the study based on feedback from providers and qualitative observations of handoffs conducted as part of other research projects. The primary objective (comparison of contact versus noncontact) will be unaffected. The total number of ACT-postoperative provider contacts is limited by the staffing of the ACT and alert fatigue in the postoperative provider. We may adjust the screening threshold to avoid overwhelming either provider. We will record PACU participation, and if participation in handoff has been low, or the overall subjective utility is low we will revisit the method of ACT-postoperative provider communication. We anticipate small improvements and changes to the underlying risk prediction algorithm. This is required because of ongoing changes in the data sources that feed into the algorithm, changes in documentation practices, and periodic need to re-calibrate predictions based on changes in unmeasured risk factors. We will update the information provided with the report card to reflect any such changes.

#### 4.3.5 Adherence

Crossover from non-contact to contact will not occur because report cards are not generated for these patients. Our outcome survey will detect if providers believe they used the report, but no other encouragement to use it will be provided. Cross-over into non-contact (failing to contact the correct provider) will be minimized by appropriate training to ACT clinicians.

### 4.3.6 Concomitant Care

ACT-intraoperative provider contact will be directed by clinical protocol. Intra- and postoperative care will be directed by the responsible physicians without any restrictions from this trial.

#### 4.4 Outcomes

# **4.4.1 Primary Outcome Measures**

The primary outcome will be self-reported handoff effectiveness.

The following survey questions will be asked of postoperative providers:

Did you receive at handoff all the information you needed to safely take care of this patient?

[Yes, No]

Did you receive information from the team giving handoff to explicitly help you manage any potential complications or problems? [Yes, No]

If so, please list what problems / topics were discussed? [Free response]

[If with-intervention phase \* ] Did you look at or discuss the postoperative report card for this patient? [Yes, No]

[If  $^*$  yes] Did the report card contain any information that was notably misleading or incorrect?

[Yes, No]

[If yes, please describe: text box]

[If \* yes] Are there any important pieces of information that the computer should have included in the report card but didn't?

[Yes, No]

[If yes, please describe: text box]

[If \* yes] How much did the ML report change questions asked or information transfer at handoff?

[ Not applicable , Not at all , a little , a fair amount , a great amount ]

[If \* yes] How much effort was accessing the report card? [Very easy, easy, some effort, hard, unable to get to it or had to ask for help]

[If \* yes] Was the information presentation in the report card easy to understand? [Easy, some effort, hard to understand, unable to use or had to ask for help]

[If \* yes] Was the information in the report card relevant?
[a great amount, a fair amount, modestly, mostly not, not at all, not sure]

[If \* yes] Was the information in the report card useful to decision making or helpful to your understanding of the patient?
[a great amount, a fair amount, modestly, mostly not, not at all, not sure]

The following questions will additionally be asked of PACU resident physicians:

Did you participate in handoff for this patient? [Yes, No]

Did you visit this patient's bedside or speak to their nurse before being asked to sign them out? [Yes, No]

Figure 7 illustrates the RedCAP survey for safety questions which will be included throughout the study.

Figure 7: RedCAP Safety Survey

Postoperative Al Risk Report Card	Resize font:  Returning?
This form is to collect reports of problems with the Al generated risk estimat study PI at [contact] if this doesn't cover your needs. The for does try to link to a patient so that we can figure out what caused the proble appreciate all feedback. The study team will never try to figure out who subn you.	rm doesn't track who you are (it is anonymous) but it em. This is an experiment (IRB: 202103210) and we
This form is to report safety problems with the Al postoperative risk report it does try to link to a patient so that we can determine what happens is approved for HIPAA-protected information.	
This field should auto-populate with a study ID from the link you followed to get here. Otherwise, (1) if you have a QR code with the email me link, and you are at a machine with a barcode scanner, click in the below field and scan the QR code (2) this is a HIPAA-protected portal, you can enter any of the Epic patient IDs and the study team will link it to the correct person.  * must provide value	d46e6e6bb147f7ebdf645e2e9be156172c32897e  Expand
Common problems:	☐ The report card is for the wrong patient ☐ The report card generated on a non-surgical patient ☐ The report card generated too early (preop) ☐ The report card generated too late (not immediately postop) ☐ The risk estimates are too low ☐ The risk estimates are too high ☐ The risk estimates were otherwise confusing ☐ The report card does have / use data that I think it should ☐ The report card has incorrect data ☐ The report card display / formatting was broken
This problem made the report card unsafe  * must provide value	○ Yes ○ No reset
Tell us anything about the problem	
	Expand
If you have comments or suggestions that aren't a problem w	vith the report card, include them here

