## 2 Objectives

The objectives of the study are to determine the interpretability, workflow role, and effect on communications of showing report cards containing ML-based risk profiles based on pre- and intra-operative data to postoperative providers.

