### 4.5 Sample Size

Precision on the absolute rate of clinician-rated inaccurate reports depends on the rate, but for 0/150 clinically inaccurate reports, the upper 95% confidence limit is 2.4%. Handoff surveys will be dichotomized into (un)acceptable. If the baseline rate of "acceptable" handoff is 70%, 50 patients without and 100 patients with intervention implies an 18% absolute increase as the minimum change with 80% power. The study is designed primarily to assess the perceived safety and workflow integration of the report card, not any patient outcomes.

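### The access-effort question goes only to providers who say they saw or discussed the report card, so the survey cannot tell failed access from other non-use

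*Combined protocol and SAP*

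**What the plan says.** The survey in section 4.4.1 (Primary Outcome Measures) puts two handoff questions to every postoperative provider. On with-intervention days it then asks "Did you look at or discuss the postoperative report card for this patient? [Yes, No". That question carries an asterisk, and a block of follow-up items is shown only if the answer to it is Yes. One of these is "How much effort was accessing the report card? [Very easy, easy, some effort, hard, unable to get to it", where the last option also covers asking for help. The others cover errors, omissions, change in questions asked, understanding, relevance and usefulness. Nothing further about the card is asked of a provider who answers No.

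Workflow is among the study's stated aims. Section 2 sets out to "determine the interpretability, workflow role, and effect on communications of showing report cards", and section 4.5 describes the study as "designed primarily to assess the perceived safety and workflow integration of the report card". On uptake, section 4.3.5 says: "Our outcome survey will detect if providers believe they used the report, but no other encouragement to use it will be provided". Section 4.3.4 says that the method of communication will be revisited if PACU participation in handoff, or the card's subjective utility, is low.

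**The concern.** The worst level of the access item shows that the authors meant to count providers who could not reach the card. The skip rule removes most of the people for whom that level was written. A provider who looked for the card, could not find or open it, and did not discuss it truthfully answers No and is sent past the item.

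Two things are at stake. First, the distribution of access effort, if reported on its own, describes only people who got to the card or at least talked about it. Second, the No answers merge three groups: providers unaware that there was a card, those who tried and failed, and those who saw no need. These call for different responses (education, a delivery repair, or a change of content). The review of the communication method in section 4.3.4 would have no structured survey data to choose between them.

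**Working it through.** No figure in the plan depends on this item, so there is none to reproduce. The check has two parts: tracing the branching, and an illustration on assumed rates.

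**Branching on a with-intervention day**

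| Provider's experience | Answer to the filter question | Access item shown? | Failure recordable there? |
|---|---|---|---|
| Opened the card | Yes | Yes | Not applicable |
| Could not open it, but discussed it | Yes | Yes | Yes |
| Could not open it, did not discuss it | No | No | No |
| Not aware of it, or chose not to look | No | No | Not applicable |

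The last two rows leave identical records. The asterisk could be read as marking only the with-intervention condition, but the follow-up condition requires a Yes, which fits only the Yes/No question.

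**Other sources in the protocol**
- Section 4.3.3: access is logged by IP address. This gives no reason for non-access.
- Section 5.3: never-accessed status is used only to exclude patients from exploratory per-protocol analyses.
- Section 4.4.1, Figure 7: the safety form lists timing, data and formatting problems and has free text, but no box for failing to find or open the card.
- Section 4.4.2: up to 150 observed handoffs with optional clarifying questions, and 20 to 30 interviews on handoff effectiveness and usefulness. Access is not a named topic.

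None is specified as a measure of failed access.

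**Illustration (all three rates are assumptions)**
- f = share of respondents who tried and failed to reach the card: 5% to 30%.
- q = share of those failures who still answer Yes because they discussed it: 0% to 50%.
- u = share not using the card for other reasons: 20%.
- Successful users = 1 − f − u. For simplicity, none of them asked for help.

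Failure among those who tried = f / (f + users). Failure shown by the conditional item = fq / (users + fq).

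For f = 20%: users = 1 − 0.20 − 0.20 = 0.60. Failure among those who tried = 0.20 / 0.80 = 25%. The item shows 0 / 0.60 = 0% at q = 0, 0.05 / 0.65 = 7.7% at q = 25%, and 0.10 / 0.70 = 14.3% at q = 50%.

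| f | Among those who tried | Item, q = 0 | Item, q = 25% | Item, q = 50% |
|---|---|---|---|---|
| 5% | 6.25% | 0% | 1.6% | 3.2% |
| 10% | 12.5% | 0% | 3.4% | 6.7% |
| 20% | 25% | 0% | 7.7% | 14.3% |
| 30% | 37.5% | 0% | 13.0% | 23.1% |

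The second formula rises with q and equals the first only at q = 1. So the item understates failure among those who tried whenever any failed-access provider answers No.

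**The case against.** Making follow-up items conditional on use is ordinary survey practice, and for the content items it is right. The access item feeds neither the primary objective (section 2.1) nor the key secondary objective (section 2.2.1), and no test or power statement rests on it.

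Several stronger readings are tempting, and the documents do not support them.

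- A reader might infer that failed delivery is counted as success and that the whole workflow objective is answered too favourably. It is not: the filter question goes to every with-intervention respondent, so the non-use rate is openly available. Only its cause is missing.
- A reader might infer that access failure is invisible to the study. Observed handoffs, interviews, free text, and the education and delivery-testing phase may all bring some failures to light. Section 1 also says the surveys will be validated by observation and interview. None of these is set up to yield a failure rate.
- A reader might infer that a null primary result could not be interpreted. The two handoff questions are unconditional, and section 5.3 plans an exploratory per-protocol analysis excluding never-accessed cards. Not seen can therefore be explored apart from seen but unhelpful. What stays merged is could not reach and did not look.
- A reader might infer that the failed-access level can never be chosen. A provider who discussed the card without opening it can choose it.

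What stands of the objection is that the gap is narrow. What it does not answer is that no structured item records why a provider answered No.

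**Conclusion.** The point holds as a limited measurement gap. The access item, read alone, is biased towards easy access whenever some providers who failed to reach the card answer No. The size cannot be derived from the documents: the figures above rest on assumed rates and show direction and possible scale only. The primary handoff comparison is unaffected, and total non-use is measured. The loss is the ability to separate failed access from unawareness and from choice, which matters for the workflow aims in sections 2 and 4.5 and for the decision in section 4.3.4.

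A second weakness sits in the same item. Its worst level joins outright failure with success after asking for help, so even recorded answers do not isolate failures.

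This is a cheap improvement worth making, not a threat to the trial's main conclusion.

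**What to change.** 1. Keep the Yes condition on the content items.
2. For with-intervention respondents who answer No, add a one-tap reason: did not know there was a card; looked for it but could not find or open it; did not try or saw no need.
3. In the access item, make failure to reach the card and needing help two separate levels.
4. Report access failure from both branches over all with-intervention respondents, beside the non-use rate.

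Simply lifting the condition from the access item would not be enough: its scale has no level for someone who never tried, and its worst level would still be mixed.

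The cost is a REDCap branching edit before the evaluation phase and one extra tap for non-users. One limit remains. Section 4.3.3 places the survey link on the Epic advisory and the printout, so a provider who receives neither may not reach the survey at all. Having the research assistant present the questions, as section 4.4.2 already allows after observed handoffs, would recover some of these providers.

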### 4.2 Participants and Eligibility

#### 4.2.1 Inclusion criteria

• Adults undergoing OR procedures in BJH South campus, including all of "Pod 2", "Pod

- 3", "Pod 5" and excluding all procedure suites such as Interventional Radiology, Parkview Tower "Pod 1", Center for Advanced Medicine "Pod 4", Labor and Delivery suites.
- Surgical service is "Acute and Critical Care Surgery", Otolaryngology, Hepato-biliary, Vascular, or Abdominal Transplant
- Planned non-ICU disposition ("floor" and "observation unit" collectively "ward" patients).
- Calculated risk of unplanned ICU admission in the first 7 postoperative days in the top 15% of historical records.

Risk of unplanned ICU admission will use the same calculator currently employed in the ACT. Risk factors considered include the surgery performed, demographics, laboratory values, comorbidities, vital signs, and medications.

Although patients are exposed to effects of the intervention, data is obtained from healthcare providers. Included providers are PACU nurses, PACU anesthesiology physicians, wards nurses, and wards midlevel providers (resident physicians, physician assistants, and advanced practice nurses) who are involved in a postoperative handoff for these patients.

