# 4.3.1 ML Report Card

The core intervention is the ML report card containing predictors of adverse events. Figure 4 is an example of the printed report card on a simulated patient. No personally identifiable information is included, other than a randomized study ID. The report card includes the operating room and date, to allow providers to know that it is for the current patient. Because the printouts are only created in operating rooms and PACU, this is sufficient information to place it in the correct chart. However, at other times the report card itself does not contain sufficient information for anyone without the studyID-patientID mapping file or pre-exising access to the EHR to determine the patient. Operating room number and time is included, but these can not be mapped to patients without the detailed surgical schedule in the EHR. The QR

code study links to an anonymous survey (no patient or provider information) for problems with the report card for the education and testing phase. The evaluation phase survey includes the additional questions in the appendix (triggered on date.

The ML risk profile generated for each patient will include risk of 30 day mortality, pulmonary complications and respiratory failure, acute kidney failure, transfusion, deep venous thrombosis, cardiac complications, and unplanned ICU admission. Additional predicted outcomes may be added based on feedback from healthcare team members. Risk profiles will display the average for all patients undergoing the same surgery, the risks calculated using preoperative assessments only (i.e. excluding intraoperative data), and the end-of-case values (i.e. including preoperative and intraoperative data). Literature-based estimates of probability of postoperative nausea and vomiting and severe postoperative pain will also be included where elevated. Expert-curated summaries of important variables will be included in the Epic report card, which include: estimated blood loss, fluids given, opioids given, duration of anesthesia, antibiotics given. Explanatory tools for the risk profile will also be generated based on SHAP values [Lundberg 2017] identifying the variables with greatest influence on predictions

Figure 4: Example ML report card

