#### Please place this with the preop/pacu signout sheet

#### Generated at 06/20/2022, 12:11:07 PM for Room: BJH OR POD 3 ROOM 302

This is an experimental (IRB: 202103210) integration of AI to identify high risk postop patients. This does not replace usual handoff, but if risks below are high, it may be worth adding the plan and assessment to your handoff. Many factors are not included in the prediction models; always use your clinical judgement. With concerns or questions please contact [contact]. Please use the QR code to take an anonymous survey (no PHI, phone is ok). For BJH computers with a scanners, open chrome, click the address bar, and scan; some scanners add a leading and trailing slash. We really feedback to make it work better! I can also be reached at [contact].

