#### Methods note

Risks generated using pre-anesthesia assessment, major comorbidities, laboratory values, and preoperative vital signs; errors in these values can significantly affect the calculations. Risk calculations use gradient boosted decision trees trained on BJH inpatient data 2019-2021. see https://pubmed.ncbi.nlm.nih.gov/31558311/

study ID 86915c307cbd5e01531052a04ff901d94371e8bf

The ACT detects that cases are near completion and that a report card should be triggered in two ways. First, the circulating nurse in each room electronically marks that a room is "close" in the EHR, usually during closure, to ensure that subsequent patients are called to the preoperative area and supplies for the next case are readied. This is performed with high fidelity as it is considered important to prevent case delays. The displayed OR schedule in Epic changes color, making this easily recognized. Second, an algorithm detects when changes in the anesthesia record suggest that the case is concluding. Both of these features cause the ML dashboard in the ACT (Figure 5) to highlight the patient as needing review to validate the report card. After manual validation, the report card will print directly in the operating room and a notification is sent to the circulating nurse to add it to the chart and provide it to the anesthesia team for handoff. The risk profile is then made active in a Best Practice Advisory in Epic.

-	nesthesia Control Tower ML Dash eview." Additional columns not sho			formation reda	acted. Yello	w highli	ght implies
Room Name	Description	akigr1\$	cardiac \$	death_in_3d=	DVT_PE\$	ICU \$	post_dialysis
BJH OR POD 2 ROOM 209	###LAPAROSCOPIC CHOLECYSTECTOMY	2.90%	1.60%	0.10%	8.80%	5.20%	0.10%
BJH OR POD 3 ROOM 301	EXPLORATION LIVER TRANSPLANT WITH WASHOUT LIVER BIOPSY AND BILE DUCT REVISION	67.10%	6.90%	7.60%	1.20%	93.40%	0.90%
BJH OR POD 2 ROOM 211	TRACHEOSTOMY PERCUTANEOUS	40.30%	2.70%	3.50%	7.40%	94.50%	0.20%

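### The plan shows no survey item for which handoff is rated or by whom, and the primary test pools all answers, so a difference in respondent mix between day types could mimic or hide an effect

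*Combined protocol and SAP*

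**What the plan says.** **Who is surveyed.** Section 4.2.1: "Included providers are PACU nurses, PACU anesthesiology physicians, wards nurses, and wards midlevel providers". Sections 1 and 4.4.2 make clear that two successive handoffs are in scope, OR to PACU and PACU to ward.

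**What they are asked.** Section 4.4.1 treats these respondents as one group: "The following survey questions will be asked of postoperative providers". The first item reads "Did you receive at handoff all the information you needed to safely take care of this patient". It does not name the handoff. The only role-specific provision is "The following questions will additionally be asked of PACU resident physicians", and the plan does not say how residents are recognised.

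**What the record holds.** Under 4.3.3 the link is specific to patient and date through a randomized study ID. Section 7.3 says that surveys collect no identifying information and that answering is voluntary.

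**How the survey arrives.** Section 4.3.3 puts the link and QR code on the Epic advisory and the printout. Section 4.3.5 says that no report card is generated for non-contact patients. The Non-Technical Summary says that handoff outcomes are still assessed on without-intervention days, but the route is not described.

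**How it is analysed.** Section 5.3 compares acceptable rates by chi-square tests on contingency tables, with no stratification.

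**The concern.** The primary rate averages over two handoffs with different givers, receivers and settings. Nothing in the plan says that their baseline acceptability is equal. If the share of answers about each handoff is the same on both day types, the average is hard to interpret but the comparison is fair. If the shares differ, the difference in mix enters the comparison directly.

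The plan gives a reason to expect unequal shares. The described carrier of the survey exists on with-intervention days and not on the others, so respondents must be reached in different ways. Neither the size nor the direction of any imbalance can be worked out from the documents.

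Two things are at stake. A mix difference could appear as a card effect or cancel a real one. And even with balanced shares, the sponsor could not say which handoff the card changed. Because responses are anonymous, a handoff or role field that was not collected could not be dependably rebuilt afterwards.

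**Working it through.** **The plan's own figure.** The plan gives no figure for respondent mix. The nearest is in 4.5: from a 70% baseline, 50 v 100 patients detect an 18-point increase with 80% power. With a pooled-variance test at 5% (the plan states neither alpha nor sidedness), the detectable increase comes out at 18.9 points two-sided and 17.2 one-sided. That is a separate matter, and nothing below depends on it.

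**Inputs from the plan**
- Baseline acceptable rate: 70% (4.5).
- Group sizes: 50 v 100 (4.5).
- Evaluation phase: 350 patients over 30 without-intervention and 60 with-intervention days (4.2.2). At equal patients per day, 350 × 30/90 ≈ 117 and 350 × 60/90 ≈ 233.

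**Assumptions, because the plan gives no values**
- One handoff type is acceptable 80% of the time and the other 60%. At a 50:50 mix this gives the plan's baseline: 0.5 × 80 + 0.5 × 60 = 70%.
- The card has no effect on either handoff.
- There is one independent response per patient, and the test is a Pearson chi-square at two-sided 5% without continuity correction.

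**Step 1: apparent rate.** With share w for the higher-rated handoff, rate = w × 80 + (1 − w) × 60.
- w = 0.5: 70%
- w = 0.7: 0.7 × 80 + 0.3 × 60 = 74%
- w = 0.8: 0.8 × 80 + 0.2 × 60 = 76%

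**Step 2: rejection rate.** Sum Bin(x; n₁, p₁) × Bin(y; n₂, p₂) over all pairs (x, y) whose chi-square exceeds 3.841.

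| Assumed rates | Share on without → with days | Apparent difference | 50 v 100 | 117 v 233 |
|---|---|---|---|---|
| 80% / 60% | 50% → 50% | 0 | 5.1% | 5.0% |
| 80% / 60% | 50% → 60% | +2 | 6.0% | 6.9% |
| 80% / 60% | 50% → 70% | +4 | 8.6% | 12.7% |
| 80% / 60% | 50% → 80% | +6 | 13.2% | 22.9% |
| 85% / 55% | 50% → 70% | +6 | 13.2% | 22.9% |
| 90% / 50% | 50% → 70% | +8 | 19.8% | 37.4% |

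**Step 3: the other direction.** If the share falls to w = 0.3 on with-intervention days, the rate with no effect is 0.3 × 80 + 0.7 × 60 = 66%, an apparent loss of 4 points. A true gain of 4 points in each handoff would then read 0.3 × 84 + 0.7 × 64 = 70% against 70%, that is, no effect.

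**The case against.** **The full instrument is not visible.** Sections 4.3.1 and 5.1 point to survey material in an appendix, and the appendix supplied holds only the observation guide. Section 4.4.1 lists questions, not every REDCap field. A reader might infer that role is never recorded and that the two handoffs can never be separated. The documents do not support that. The resident branch implies some recognition of role, and surveys presented after an observed handoff (4.4.2) could be labelled. This stands, and it limits the point to what the plan shows. Labelling observed handoffs would still leave the other responses unlabelled.

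**The anonymity statements do not rule out a role field.** The Figure 7 form is the safety survey, and the statement in 4.3.1 that no provider information is held describes the education-and-testing survey. Section 7.3 excludes identifying information, and broad role does not identify anyone. This also stands. It means that the proposed item fits the plan.

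**Handoff givers.** Section 4.3.1 says "a notification is sent to the circulating nurse to add it to the chart and provide it to the anesthesia team for handoff", so a reader might infer that those giving the handoff answer the survey on with-intervention days. That is conjecture. Section 4.2.1 does not list them, and the items are worded for receivers.

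**A tilt toward the PACU.** The text message to the PACU resident and the filing with the signout sheet might suggest that PACU answers dominate on with-intervention days. But the rule in 4.3.1 against direct contact covers PACU nurses as well as ward providers, and the Epic advisory can reach ward staff. No direction can be claimed.

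**Size.** The rates and mixes are assumed, and 4 points is small beside the 18 in 4.5. This is fair. The calculation shows how the mechanism works; it is not a forecast.

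**Conclusion.** The point holds in this form: the documents show no item recording which handoff is rated or the respondent's role, beyond an undescribed resident branch, and the primary test pools everything. A mix difference by day type is plausible because the described survey carrier is missing on without-intervention days. Such a difference would pass straight into the primary comparison.

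In the main illustration the spurious difference is 4 points, with rejection of 8.6% at 50 v 100 and 12.7% at 117 v 233 in place of about 5%. This rests on the assumed 80% and 60% rates, a 20-point shift in share, independent responses and a two-sided 5% test. The real size and sign are unknown. The documents do not show that bias will occur, that it favours the card, or that the answers can never be separated.

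The change is worth making because it concerns the primary outcome and costs little, and the missing information could not be dependably recovered later.

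**What to change.** **In 4.4.1,** add one required, non-identifying item at the top of the survey on both day types:
- I received the OR-to-PACU handoff as nurse, resident or attending.
- I received the PACU-to-ward handoff as nurse or midlevel provider.
- I did not receive this handoff.

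Use the answer to route the PACU-resident questions. Leave the third category out of the primary rate, which agrees with the included providers in 4.2.1.

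**In 5.3,** make the primary comparison stratified by handoff type, for example by Mantel-Haenszel, and report acceptable rates and numbers of responses by handoff and day type.

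**Cost.** One extra click per survey, a sentence in 5.3, and a small edit to the anonymity wording to say that broad role is recorded but identity is not. If the REDCap form already holds the field, only the 5.3 change is needed. Stratifying removes differences in handoff mix. It does not correct for selective response within one handoff, so the response counts should be shown.
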